**Part 2 (Safety/Efficacy Study):**

Approximately 16 HCV GT1-infected and approximately 10 HCV GT4-infected treatment-naïve or IFN (IFN or pegIFN with or without RBV) treatment-experienced pediatric subjects in the  $\geq 12$  to 17 age group will be enrolled.

Subjects with GT1 infection will receive the 3D tablet formulation approved for adults (with or without RBV) and the subjects with GT4 infection will receive the 2D tablet formulation approved for adults with RBV. RBV will be administered weight based as tablets or as solution per local RBV label. The regimen and duration will be determined according to HCV genotype, sub-genotype and cirrhosis status.

**Methodology (Continued):**

**Part 2 (Safety/Efficacy Study) (Continued):**

Patient Population	Treatment	Duration
Genotype 1b with or without compensated cirrhosis	ombitasvir + paritaprevir + ritonavir + dasabuvir (approved adult 3D formulation)	12 weeks
Genotype 1a,* without cirrhosis	ombitasvir + paritaprevir + ritonavir + dasabuvir + ribavirin (approved adult 3D formulation plus RBV)	12 weeks
Genotype 1a,* with compensated cirrhosis	ombitasvir + paritaprevir + ritonavir + dasabuvir + ribavirin (approved adult 3D formulation plus RBV)	24 weeks
Genotype 4 with or without compensated cirrhosis	ombitasvir + paritaprevir + ritonavir + ribavirin (approved adult 2D formulation plus RBV)	12 weeks

\* Follow the genotype 1a dosing recommendations in patients with an unknown genotype 1 sub-genotype or with mixed genotype 1 infection.

Study treatment visits will occur at Day 1, Week 2, Week 4, Week 8, Week 12, Week 16, Week 20, and Week 24. The latter 3 visits at Weeks 16, 20 and 24 are required for subjects with compensated cirrhosis taking study drug for 24 weeks. PT visits will occur at PT Weeks 4, 12, and 24.

One PK sample (regardless of the dosing time) will be collected at each visit for each subject in Part 2.

The following criteria will be considered evidence of virologic failure during treatment. Pediatric subjects demonstrating any of the following should be discontinued from study drug:

- Confirmed increase from nadir (defined as 2 consecutive HCV RNA measurements  $> 1 \log_{10}$  IU/mL above nadir) in HCV RNA at any time point
- Confirmed HCV RNA  $\geq 100$  IU/ml (defined as 2 consecutive HCV RNA measurements  $\geq 100$  IU/ml) at any point after achieving HCV RNA  $< \text{LLOQ}$

Confirmatory testing should be completed as soon as possible. If any of the above criteria are met, the subject will discontinue study treatment, if applicable. If the Investigator feels that a subject who meets one of these criteria should still remain on study treatment, the subject would only be allowed to remain on treatment with approval of the AbbVie Study TA SD/TA MD.

**Part 3 (Long-Term Follow-Up):**

All subjects who have completed Post-Treatment Week 24 in either Part 1 or Part 2 of the study will be followed to assess the durability of viral response, for the emergence and persistence of resistant viral variants, and for SAEs related to study drug for an additional 120 weeks in the Long-term Follow-up period. Study visits will occur at Post-Treatment Weeks 36, 48, 96, and 144.

**Diagnosis and Main Criteria for Inclusion/Exclusion:**

**Main Inclusion:**

1. Male or female  $\geq 3$  to 17 years of age and weight  $\geq 15$  kg at time of enrollment.
2. Willingness to participate in the study for up to 42 months.
3. HCV infection demonstrated by positive anti-HCV Ab and HCV RNA  $\geq 1000$  IU/mL at the time of screening.
4. Screening laboratory results indicating HCV genotype 1 for enrollment into Part 1 and genotype 1 or 4 for enrollment into Part 2.
5. Parent or legal guardian with the willingness and ability to provide written informed consent and subject willing and able to give assent, as appropriate for age and country.

**Main Exclusion:**

1. Women who are pregnant, breastfeeding, or are considering becoming pregnant.
2. Use of known strong inducers and inhibitors (e.g., gemfibrozil) of cytochrome P450 2C8 (CYP2C8) in subjects receiving dasabuvir, or strong or moderate inducers of CYP3A, within 2 weeks or 10 half-lives, whichever is longer, of the respective medication/supplement prior to study drug administration.
3. Positive test result for Hepatitis B surface antigen (HbsAg) or anti-HIV antibody (HIV Ab) test.
4. Current enrollment in another interventional clinical study, previous enrollment in this study, prior or current use of any investigational or commercially available anti-HCV agents other than IFNs or RBV or receipt of any investigational product within 6 weeks prior to study drug administration.

**Investigational Products:**

Weight < 45 kg or eligible but not willing to swallow the adult formulations: Part 1	
paritaprevir	1.0 mg mini-tablet
ritonavir	1.0 mg mini-tablet
ombitasvir	0.3 mg mini-tablet
dasabuvir	3.08 mg mini-tablet
ribavirin	40 mg/mL oral solution
Weight <math>\geq 45</math> kg who are <math>\geq 12</math> to 17 years old and willing to swallow the adult formulations:	
ombitasvir/paritaprevir/r	12.5/75/50 mg tablet
dasabuvir	250 mg tablet
Ribavirin	200 mg tablet

Doses:	Part 1 Mini-Tablet:			
	Initial dosing based on body weight at time of Screening:			
		≥ 15 to 29 kg	≥ 30 to 44 kg	≥ 45 kg
	paritaprevir (QD)	50 mg	100 mg	150 mg
	ritonavir (QD)	35 mg	70 mg	100 mg
	ombitasvir (QD)	10 mg	15 mg	25 mg
	dasabuvir (BID)	100 mg	150 mg	250 mg
	Ribavirin solution	Per local label		
	Part 2:			
	Only adult formulation and RBV tablets if required will be provided to subjects who are in the ≥ 12 – 17 year old age group with weight equal and greater than 45 kg and willing to swallow the adult formulations.			
Mode of Administration:	Oral			
Reference Therapy:	Not applicable			
Dose:	Not applicable			
Mode of Administration:	Not applicable			
Duration of Treatment:	Part 1: Pediatric subjects will receive OBV, PTV, RTV, DSV with or without RBV for 12 weeks.			
	Part 2: Pediatric subjects will receive OBV, PTV, RTV with or without DSV and with or without RBV for 12 weeks or 24 weeks.			
Criteria for Evaluation:	Efficacy:			
	Plasma HCV RNA (IU/mL) will be assessed at each treatment and Post-Treatment Period visit in all three parts of the study.			
	Pharmacokinetic:			
	Plasma concentrations of OBV, possible OBV metabolites, PTV, possible PTV metabolites, DSV, DSV M1 metabolite, other possible DSV metabolites, RTV and RBV (if applicable) will be determined at each study visit for each subject for the treatment periods of Part 1 and Part 2.			
	Safety:			
	Safety and tolerability will be assessed by monitoring adverse events, physical examinations, clinical laboratory tests and vital signs. Growth and development will be assessed relative to age specific norms.			

**Statistical Methods:**

The pharmacokinetic analysis will be performed separately for Part 1 and Part 2. For population pharmacokinetic analyses, data from Part 1 and Part 2 will be combined if needed. All efficacy, safety, growth and development outcomes will be assessed across Parts 1 and 2 of the study with summaries by formulation, age and weight group, totaled across all subjects, and totaled across adult formulations (OBV/PTV/RTV + RBV and OBV/PTV/RTV and DSV ± RBV). Analyses on durability of response, resistance, growth and development outcomes, and patient-reported outcomes will be performed through Post-Treatment Week 24 in Parts 1 and 2 and after Post-Treatment Week 24 for all subjects in Part 3.

An interim analysis will occur once all subjects complete PT Week 12 or prematurely discontinue from the study. Final analysis will occur after the completion of the whole study.

**Efficacy:**

The primary pharmacokinetic endpoints are  $C_{max}$  and AUC following dosing on Week 2, and trough concentration ( $C_{trough}$ ) following dosing on Week 2 and Week 8 for OBV, PTV, DSV, and RTV.

The primary efficacy endpoint is the percentage of subjects with SVR12 among all subjects. The percentage of subjects achieving SVR12 will be calculated along with the 2-sided 95% confidence interval. The lower bound of the 2-sided 95% confidence interval of the percentage of subjects with SVR12 across all subjects must be greater than 67% to show superiority to pegIFN and RBV as described in Section 8.2.

The main secondary endpoints are:

1. The percentage of subjects who achieve SVR12 summarized by formulation, age and weight group and across all subjects.
2. The percentage of subjects who achieve SVR24 by formulation, age and weight group, across all the subjects, and across all subjects on the adult formulations;
3. The percentage of subjects with ALT normalization during treatment, defined as ALT ≤ ULN at the final treatment visit for subjects with ALT > ULN at baseline, by formulation, age and weight group, across all subjects, and across all subjects on the adult formulations.

For the secondary efficacy endpoints, the simple percentage will be calculated along with the 2-sided 95% confidence interval. For both primary and secondary endpoints, the normal approximation to the binomial distribution will be used if the rate is not 0% or 100%, otherwise the Wilson's score method will be used to calculate the confidence interval. The lower bound of the 2-sided 95% confidence interval of the SVR24 rate across all subjects in the study will also be compared to 67%.

**Resistance:**

For subjects with virologic failure and HCV RNA > 1000 IU/mL, the variants at each amino acid position (by population, deep, and/or clonal nucleotide sequencing) at available post baseline time points compared to baseline and prototypic reference standard sequences will be summarized by DAA target genes and accompanying listings will be provided.

**Statistical Methods (Continued):**

**Safety:**

All safety analysis will be done by age and weight group separately for each formulation, for all subjects, and for all subjects on the adult formulations.

The number and percentage of subjects reporting treatment-emergent adverse events will be tabulated by MedDRA system organ class and preferred term. Tabulations will also be provided in which the number of subjects reporting an adverse event (MedDRA preferred term) is presented by grade (Grades 1 – 5) and relationship to study drugs.

Change from baseline in laboratory tests and vital sign measurements to each time point of collection will be summarized descriptively. Laboratory test and vital sign values that are potentially clinically significant, according to predefined criteria, will be identified and the number and percentage of subjects with potentially clinically significant values during treatment will be calculated.

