**Methodology:**

The study aims to assess three formulations in the pediatric population. The approved adult 3D (OBV/PTV/RTV and DSV) regimen formulation and the approved adult 2D (OBV/PTV/RTV) regimen formulation will be administered in subjects who are in the  $\geq 12$  to 17 years old age group with weight greater than 45 kg and willing to swallow the adult formulation. The mini-tablet formulation will be administered in subjects who are in the  $\geq 3 - 8$  and  $\geq 9 - 11$  age groups to identify the optimal or final doses.

Part 1 mini-tablet is designed to allow for dose adjustment on an ongoing basis, based on available pharmacokinetic and clinical data to achieve therapeutic exposures that have been safe and efficacious in adult subjects. Area under the concentration curve (AUC) from the intensive PK sampling at Week 2 will be the primary measure for dose adjustment, which will be compared with the range of the geometric means and the range of individual values across Phase 1/2/3 studies in adults that had intensive PK data (see Section 5.1).  $C_{max}$  and  $C_{trough}$  will be considered for safety and efficacy using the same rules. Part 2 (Safety and Efficacy) will use the adult formulation if the results from the adult formulation in Part 1 are satisfactory. In Part 1 and Part 2, the treatment duration is either 12 weeks or 24 weeks and all pediatric subjects who receive at least 1 dose of study drug will be followed for 24 weeks in the post-treatment period after completing or prematurely discontinuing the study treatment. All pediatric subjects who complete the Post-Treatment (PT) Week 24 visit in either Part 1 or Part 2 will be followed in Part 3 (Long-term Follow-up) for 144 weeks.

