### **8.1.6 Safety**

All subjects who receive at least one dose of study drug will be included in the safety analyses. The safety analysis will be carried out for all subjects by formulation, age and weight group, for all subjects on the adult formulation. A listing of any SAEs recorded in Part 3 will be included.

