**Methodology:**

The study aims to assess three formulations in the pediatric population. The approved adult 3D (OBV/PTV/RTV and DSV) regimen formulation and the approved adult 2D (OBV/PTV/RTV) regimen formulation will be administered in subjects who are in the  $\geq 12$  to 17 years old age group with weight greater than 45 kg and willing to swallow the adult formulation. The mini-tablet formulation will be administered in subjects who are in the  $\geq 3 - 8$  and  $\geq 9 - 11$  age groups to identify the optimal or final doses.

Part 1 mini-tablet is designed to allow for dose adjustment on an ongoing basis, based on available pharmacokinetic and clinical data to achieve therapeutic exposures that have been safe and efficacious in adult subjects. Area under the concentration curve (AUC) from the intensive PK sampling at Week 2 will be the primary measure for dose adjustment, which will be compared with the range of the geometric means and the range of individual values across Phase 1/2/3 studies in adults that had intensive PK data (see Section 5.1).  $C_{max}$  and  $C_{trough}$  will be considered for safety and efficacy using the same rules. Part 2 (Safety and Efficacy) will use the adult formulation if the results from the adult formulation in Part 1 are satisfactory. In Part 1 and Part 2, the treatment duration is either 12 weeks or 24 weeks and all pediatric subjects who receive at least 1 dose of study drug will be followed for 24 weeks in the post-treatment period after completing or prematurely discontinuing the study treatment. All pediatric subjects who complete the Post-Treatment (PT) Week 24 visit in either Part 1 or Part 2 will be followed in Part 3 (Long-term Follow-up) for 144 weeks.

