### **5.0                   Analysis Populations**

#### **5.1                   Definition for Analysis Populations**

##### **5.1.1               Intention-to-Treat (ITT) Population**

The intention-to-treat (ITT) population will consist of all subjects who receive at least one dose of study drug in Part 1 or Part 2 of the study. All data from Part 1, Part 2, and Part 3 will be combined together, as appropriate, for statistical analyses specified in the SAP.

Demographic, baseline characteristic, exposure, concomitant medication and medical history analyses will be performed in the ITT population by age and weight group and overall among subjects on the mini-tablet formulation (ITT mini-tablet table with 6 columns), and in summary tables, by Part 1 vs Part 2 and overall for subjects on the adult formulation and overall among subjects on the mini-tablet formulation, and overall among all subjects (ITT summary table with 5 columns). Efficacy endpoints, growth and

development outcomes, and patient reported outcomes will be summarized in the ITT population. Acceptability questionnaire will be summarized overall and by age group among subject on the mini-tablet formulation in the ITT population.

In addition, sensitivity analyses of the percentage of subjects with SVR12, will be performed on the Modified Intent-to-Treat Genotype (mITT-GT) population, and Modified Intent-to-Treat Genotype and Virologic Failure (mITT-GT-VF) population, respectively, as defined below.

The mITT-GT population includes subjects who receive at least 1 dose of study drug in Part 1 or Part 2 but excludes the subjects in Part 1 who are not of HCV GT1 infection and subjects in Part 2 who are not of HCV GT1 or GT4 infection. The mITT-GT population is used to reduce the risk of bias that could occur due to enrolled population deviating from the treatment regimen as specified by the protocol.

The mITT-GT-VF population includes all subjects who receive at least 1 dose of study drug but excludes the subjects in Part 1 who are not of HCV GT1 infection and the subjects in Part 2 who are not of HCV GT1 or GT4 infection and in either part excludes subjects who did not achieve SVR12 for reasons other than on treatment virologic failure or relapse. The mITT-GT-VF population is used to reduce the risk of bias that could occur due to either discordant HCV genotype or failures unrelated to study drug.

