### **5.1.2 Safety Population**

All subjects who receive at least one dose of study drug in Part 1 or Part 2 will be included in the safety population, which will be the same as the ITT population for this study.

Safety analyses will be performed on the safety population by age group and overall among subjects on the mini-tablet formulation, by Part 1 vs Part 2 and overall among subjects on the adult formulation, and overall among all subjects (Safety Summary 7 column table).

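### The SAP's safety table layout pools the adult 2D and 3D tablets, so no safety count or percentage is tabulated for the roughly 10 subjects on 2D + RBV

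*Protocol*

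**What the plan says.** **Protocol.** The synopsis, under Methodology, states "The study aims to assess three formulations in the pediatric population". It then names two adult ones: "The approved adult 3D (OBV/PTV/RTV and DSV) regimen formulation and the approved adult 2D (OBV/PTV/RTV) regimen formulation will be administered" to adolescents, with the mini-tablet as the third. SAP Section 4.2 repeats the count of three. Under Statistical Methods, the synopsis asks for efficacy and safety summaries by formulation, age and weight group, and for results "totaled across adult formulations (OBV/PTV/RTV + RBV and OBV/PTV/RTV and DSV ± RBV". Its safety paragraph reads "All safety analysis will be done by age and weight group separately for each formulation, for all subjects", followed by a total for everyone on the adult formulations. Section 8.1.6 is looser: "The safety analysis will be carried out for all subjects by formulation, age and weight group, for all subjects on the adult formulation".

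**SAP.** Section 5.1.2 fixes one layout. The mini-tablet part is: "Safety analyses will be performed on the safety population by age group and overall among subjects on the mini-tablet formulation". The adult part and the grand total are: "by Part 1 vs Part 2 and overall among subjects on the adult formulation, and overall among all subjects (Safety Summary 7 column table". Section 8 (disposition), Section 9 (exposure and compliance) and Section 11.1 (safety) all adopt this layout. The summary ITT table in Section 5.1.1, used for baseline data, treats the adult tablets in the same way: "by Part 1 vs Part 2 and overall for subjects on the adult formulation and overall among subjects on the mini-tablet formulation", plus all subjects.

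**The concern.** Both documents define two adult formulations, but the SAP's safety layout treats them as one and divides it by study part. That division does not recover the regimens. Part 1 adult-tablet subjects all receive 3D. Part 2 mixes genotype 1 subjects on 3D with genotype 4 subjects on 2D + RBV. So no column holds 2D alone and none holds all of adult 3D. A ribavirin split would not isolate 2D either, because genotype 1 subjects who are not 1b take ribavirin with 3D (Protocol Table 6).

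Protocol Section 3.1 describes this as the first study of these regimens in children, and 2D is given only in Part 2. The adult evidence for 2D is also thinner. Section 3.2 cites 135 adults with genotype 4 for 2D, against more than 2,300 adults with genotype 1 for 3D. A reader who wants the adverse-event, laboratory or discontinuation rate on 2D in adolescents would find no table that gives it.

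**Working it through.** **Inputs**
- Part 1 subjects on adult tablets, all 3D: 12 (Protocol synopsis, Part 1; SAP Section 4.2 says at least 12).
- Part 2: about 16 genotype 1 subjects on 3D and about 10 genotype 4 subjects on 2D + RBV (Protocol synopsis, Part 2; SAP Section 4.2).
- Total: about 62.

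**1. Reproduce the SAP's column counts.**
- Safety layout: mini-tablet 2 age groups + overall = 3; adult Part 1 + Part 2 + overall = 3; all subjects = 1. 3 + 3 + 1 = 7, the number the SAP states. There is no unlisted 2D column.
- ITT summary: adult Part 1 + Part 2 + overall = 3; mini-tablet overall = 1; all subjects = 1. 3 + 1 + 1 = 5, again the stated number.

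**2. Where the 2D subjects sit.**
- Part 2 column: 10/(10 + 16) = 10/26 = 38%.
- Adult total: 10/(12 + 16 + 10) = 10/38 = 26%.
- All subjects: 10/62 = 16%.

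**3. What pooling can hide (assumed events, for illustration only).**
- If 3 of 10 on 2D and none on 3D have an event, 2D is at 30% and 3D at 0%. The tables show 3/26 = 11.5% in Part 2 and 3/38 = 7.9% in the adult total.
- With assumed underlying rates of 30% on 2D and 5% on 3D, the expected table entries are (10 × 0.30 + 16 × 0.05)/26 = 3.8/26 = 14.6% and (10 × 0.30 + 28 × 0.05)/38 = 4.4/38 = 11.6%.
- With the rates reversed, they are (10 × 0.05 + 16 × 0.30)/26 = 5.3/26 = 20.4% and (10 × 0.05 + 28 × 0.30)/38 = 8.9/38 = 23.4%.

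The last two cases are expectations, not whole-subject counts.

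**4. What a separate 2D column could say.** With 0/10 events, the exact two-sided 95% upper bound is 1 − 0.025^(1/10) = 30.8%. The Wilson bound is 27.8%.

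**5. Column counts after the change.** Five adult columns replace three, so the safety layout goes from 7 to 9 and the ITT summary from 5 to 7.

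**The case against.** **The word *formulation* is not used consistently.** Protocol Table 10 uses it for dosage form (tablets, mini-tablets, solution) and lists a single OBV/PTV/RTV tablet for both parts, so 2D is that tablet without dasabuvir. Section 8.1.2.5 sets the adult formulations against the mini-tablet. Section 8.1.6 and the SAP use the singular for the adult tablets. On that usage, a layout of mini-tablet versus adult already reports by formulation. This stands as a real ambiguity, so a reader should not infer a plain breach of an unambiguous protocol rule. It does not remove the conflict. The synopsis and SAP Section 4.2 count three formulations, and the synopsis defines the adult total as a sum over 2D + RBV and 3D ± RBV.

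**A reader might infer that 2D gets no safety output at all.** The documents do not support that. The SAP plans a listing of treatment-emergent events with subject numbers (Section 11.2.1.1) and listings of serious events, discontinuations, interruptions and ribavirin modifications (Section 11.2.2). It also plans laboratory listings for subjects who meet the potentially-clinically-significant criteria (Section 11.3.2) and liver-test listings for those who meet the hepatic criteria. With about 10 subjects, 2D events could be picked out by hand. What is missing is a planned count and percentage.

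**A reader might extend the point to efficacy.** SAP Sections 10.4, 10.7 and 10.8 present efficacy by formulation, and Section 10.5 gives SVR12 by genotype, where genotype 4 means 2D + RBV. Section 11 has no such genotype split.

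**A reader might also infer a confounded Part 1 versus Part 2 safety comparison.** None is planned; the columns are descriptive. Part 2 also admits cirrhosis, prior interferon treatment and 24-week treatment, so separating 2D would not make the two parts comparable.

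**Conclusion.** The point holds as a gap in tabulated safety results. The plan produces no safety, disposition, exposure or compliance summary for 2D + RBV, although the more specific protocol text calls for safety by each formulation and treats 2D as one. The pooling affects about 38% of the Part 2 column and 26% of the adult total.

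These shares assume that Part 2 enrols 16 and 10 as planned and that 12 subjects take adult tablets in Part 1. The masking figures rest on assumed events and show direction, not expected results. The conclusion also depends on reading *formulation* as the synopsis and SAP Section 4.2 do. Under the dosage-form reading there is no formal conflict, but a tabulated 2D result is still missing.

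The primary endpoint is unaffected. A 2D column would be descriptive: an upper bound of 31% for 0/10 does not exclude the 30% rate used in the illustration. It should not be used to compare 2D with 3D, because every 2D subject takes ribavirin and only some 3D subjects do. The change is worth making before the tables are programmed, but the trial's main conclusion does not depend on it.

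**What to change.** In SAP Section 5.1.2, replace the three adult columns with five: 3D Part 1, 3D Part 2, 3D total, 2D + RBV and adult total. Use that layout wherever Sections 8, 9 and 11 call for the safety format. Make the same replacement in the five-column ITT summary table of Section 5.1.1, so that baseline data for the 2D subjects can be read beside their safety data. State once in the SAP that *formulation* means adult 3D, adult 2D or mini-tablet, and label the 2D column as descriptive.

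The cost is SAP wording, table shells and two extra columns per table, from data already collected. The drawback is wider tables and a column of about 10 subjects whose percentages move in steps of 10 points.
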